4.1 Confidence intervals and p-values

Statistical tests and confidence intervals will be two-sided. All estimates will be presented with 95% confidence intervals. P-values will be presented where appropriate. No adjustments will be made for multiple testing; interpretations will be based on the strength of evidence of effect size and consistency of results for related outcomes.

4.2 Adherence protocol violation and deviation

We follow the standard definition of protocol violations and deviations.

Specifically we consider the following as major deviations:

- Not attending the decision visit within six months (defined as 24 weeks) after randomization
- Individuals in the control arm not receiving a VL to inform the decision visit
- Individuals in the intervention arm not receiving GRT to inform their decision visit, except for cases where GRT was not possible due to resuppression to <400 copies/mL
- Not having a VL result within the 9-month window and not having reached the primary endpoint before or at the 9-month visit (Figure 1)
- Individuals in the control arm receiving a GRT before completing the study

As violations we consider any enrolment of an individual not fulfilling the eligibility criteria at the moment of enrolment.

4.3 Analysis populations

Analyses will be performed following the CONSORT guidelines [5]. Individuals are the unit of analysis. The following analysis sets will be used in this trial:

The full analysis set (FAS) will include all participants as randomised. All statistical analyses will be performed on the modified intention-to-treat (mITT) set, which will exclude participants found to be ineligible for the study only after randomization (i.e., with violations).

A per-protocol (PP) analysis set will include all randomized participants who completed the study without a protocol violation or major deviation. The primary endpoint will also be performed on the PP analysis set.

5. Trial population

5.1 Eligibility

Screening/eligibility data will be summarized in a CONSORT flowchart, showing the total number of individuals screened and the reasons for screening failures as per eligibility criteria in section 3.1.1.

5.2 Recruitment

The CONSORT flowchart will include the numbers of participants randomized to each of the two trial arms.

5.3 Withdrawal/follow-up

The CONSORT flowchart will summarize enrolment, decision, 6, and 9-month study visit for each participant, by randomized group. Reasons will be given for participants who did not complete follow-up as expected.

5.4 Baseline patient characteristics

Baseline characteristics will be summarized by randomized group, using medians and interquartile ranges for continuous variables and numbers and percentages for categorical variables. Shell tables showing the variables and categories are included in section 8. Assessment will be made for baseline imbalances between the randomization groups by visual inspection only, by the trial team before looking at outcome data. In analyses, we will further adjust the outcome analyses for any covariates found to be imbalanced and potentially relevant to the outcome (erring on the side of inclusivity). There will be no formal testing of baseline characteristics across randomized groups [6].

6. Analysis

Time will be measured from the date of the baseline/enrolment visit.

Programming of the data analysis will be done by the trial statistician. This code for the primary outcome analysis will be checked for validity by the external independent statistician who will then use the final validated code to conduct the interim analysis.

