3.1.1 Eligibility

Eligibility criteria are as follows:

Inclusion criteria:

- In care in a study site
- Age ≥ 6 months and <19 years
- Latest HIV VL result ≥ 400 c/mL
- On an unchanged ART regimen for ≥ 6 months
- Phlebotomy for latest VL test <4 months before screening
- Consent given (see section 4.2)

Exclusion criteria:

- Indication for treatment switch according to WHO guidelines at screening
- 1st enhanced adherence counselling session initiated >2 weeks prior to screening
- Intention to transfer out of the study site (and not into a different study site) within 3 months after randomization
- Already enrolled in another study if judged as non-compatible by the (Local) Principal Investigator
- Pregnant or breastfeeding at screening (no exclusion based on pregnancy or breastfeeding after enrolment)
- Acute illness requiring hospitalization at screening (no exclusion based on hospitalization after enrolment)
- Received a resistance test within the last 12 months

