3.1.2 Objectives and Endpoints

The trial objectives are:

Primary Objective: To assess if GRT-based management of viremia in CALHIV on ART in resource-limited settings improves overall health outcomes. The results of this trial are intended to inform future WHO and national guidelines on the use of GRT in CALHIV.

Secondary Objectives: To assess the impact of GRT-based management of viremia in CALHIV on various individual health outcomes including mortality, morbidity, and virologic status.

Exploratory Objectives: To assess the dynamics of viral resuppression and the viral development of drug resistance without vs with GRT-based management of viremia.

The primary and secondary endpoints of the trial are:

Primary endpoint

The trial is powered to detect a significant reduction of the composite primary endpoint in the intervention arm compared to the control arm. The composite primary outcome is comprised of: i) death due to any cause during the follow-up period (36 weeks), ii) HIV- or ART-related hospital admission of ≥ 24 hours duration (possibly, probably or definitely related to HIV or ART, judged by the endpoint committee blinded to the study arm) during the follow-up period (36 weeks), iii) new clinical WHO stage IV event (excluding lymph node tuberculosis, stunting, oral or genital herpes simplex infection and oesophageal candidiasis; judged by the endpoint committee blinded to the study arm) during the follow-up period (36 weeks), and iv) no documentation of a suppressed VL (<50 c/mL) at 9 months follow-up (window: 32-44 weeks).

The primary endpoint will be assessed as an event ratio of participants reaching any of the above-mentioned composite endpoints.

An endpoint committee whose members are unaware of study arm assignments will review all reported WHO stage IV events and hospitalizations and determine if the events in question qualify as endpoints.

Secondary endpoints

- Separate analyses of the four components of the primary endpoint, namely:
 - Death due to any cause
 - HIV- or ART-related hospital admission of ≥ 24 hours duration (possibly, probably or definitely related to HIV or ART, judged by the endpoint committee blinded to the study arm)
 - New clinical WHO stage IV event (excluding lymph node tuberculosis, stunting, oral or genital herpes simplex infection and oesophageal candidiasis, judged by the endpoint committee blinded to the study arm)

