3.2 Randomization

Certain baseline factors may have an effect on the primary and secondary endpoints, including the site, age, gender, and the participant's ART regimen at enrolment. In order to minimise bias, randomisation was stratified by:

- Country (Lesotho or Tanzania)
- Age at enrollment ([≥ 6 months to <12 years] vs [≥ 12 years to <19 years])
- ART regimen at enrolment (NNRTI-based, protease inhibitor (PI)-based, or integrase strand transfer inhibitor (INSTI)-based regimen)

In children, gender is unlikely to have a major impact on outcomes. Given the sample size and the relatively even gender distribution (expected female to male ratio approximately

3:2), a strong clustering effect is unlikely. However, gender will be considered in the planned subgroup analysis.

Eligible and consented patients are consecutively enrolled and randomised in a 1:1 ratio to the intervention and control arms. Randomisation is stratified according to the factors listed above, using permuted blocks with varying block size. Randomisation is automated using the MACRO electronic data capture software (Elsevier; see chapters 4.3 Study procedures, and 8.2 Data recording and source data). Randomisation of a participant is performed once eligibility and consent have been confirmed and entered into the database, thereby maintaining concealment of allocation.

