6.2 Analysis methods

Continuous variables will be inspected using histograms: 1) to assess for outliers which may be queried for accuracy, and 2) to assess whether appropriate transformations are required for modeling.

Endpoints will be summarized using medians and interquartile ranges for continuous variables and numbers and percentages for categorical variables, by randomized group. Percentages will be reported to one decimal place.

We will present numbers and proportions of participants achieving each of the four components of the composite endpoint separately. Those with missing VL results will be handled as

described in section 6.1 and reasons for missing VL results will be provided.

For the analysis of the primary outcome, we will use a logistic regression model adjusted for the randomization stratification factors (country, age, and ART regimen; see section 3.2) and relevant baseline characteristics found to be unbalanced between intervention and control clusters (as described above in section 5.5). Results will be reported as odds ratios with 95% confidence intervals. Further, we will estimate the absolute risk difference, with 95% confidence intervals estimated using the delta method [7].

Sensitivity analyses

In a first sensitivity analysis for the primary outcome, we will analyze the PP set (see section 4.2). Protocol violations and deviations will be described. We will summarize the data (numbers and proportions of participants included in this analysis, and meeting the primary endpoint), and fit logistic regression models as for the main primary outcome analysis.

As a second sensitivity analysis of the primary outcome, we will also consider an additional two definitions of viral suppression - <400 and <1000 copies/mL.

Subgroup analysis

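### Beyond the three strata, the primary model takes in covariates only if they look imbalanced; entry viral load should be a pre-specified covariate, for a modest gain.

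*SAP*

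**What the plan says.** SAP 6.2 specifies a logistic model with the randomisation strata (country, age group, ART class) and, in addition, "relevant baseline characteristics found to be unbalanced between intervention and control clusters". SAP 5.4 gives the rule: "we will further adjust the outcome analyses for any covariates found to be imbalanced and potentially relevant to the outcome". Imbalance is assessed "by visual inspection only, by the trial team before looking at outcome data". A bracketed remark in 5.4 says that doubtful cases should be resolved towards inclusion. No candidate list and no threshold is given.

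On viral load, the inclusion criteria in 3.1.1 require "Latest HIV VL result ≥ 400 c/mL" and "Phlebotomy for latest VL test <4 months before screening". SAP 4.3 removes participants found ineligible after randomisation from the mITT set, so everyone in the main analysis should have an entry value. Component iv of the primary endpoint (3.1.2) is "no documentation of a suppressed VL (<50 c/mL) at 9 months follow-up".

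Entry VL is nevertheless not a named covariate. The sentence in 3.2 that begins "Certain baseline factors may have an effect on the primary and secondary endpoints, including the site, age, gender" goes on to ART regimen and does not mention VL, although its list is not put as exhaustive. Tables 8.1 to 8.3 have no VL row, while Table 8.3 lists CD4-based immunodeficiency, HBsAg, haemoglobin, leucocytes, platelets and creatinine. Section 8 presents these tables as illustrations, so they do not bar other variables.

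**The concern.** A covariate adds precision because it predicts the outcome, not because the arms happen to differ on it. Under 5.4 a covariate must be both relevant and visibly imbalanced. A relevant covariate that looks balanced is therefore left out, and its precision is forgone.

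Entry VL is the natural candidate: it is the baseline value of the quantity behind component iv, and eligibility requires it. If the shells are followed literally, it would not even be tabulated for inspection.

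Two things are at stake. The covariate set of the primary model is not known until the baseline data have been viewed, and an adjusted odds ratio is conditional on whichever covariates are chosen. Some power and precision of the risk difference is also given up.

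**Working it through.** **1. The plan's own figure.** Inputs from 3.3 and 4.1: 20% vs 35%, two-sided 5%, 80% power, Pearson chi-squared.

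n per arm = [1.960·√(2·0.275·0.725) + 0.842·√(0.20·0.80 + 0.35·0.65)]² / 0.15² = [1.960·0.6315 + 0.842·0.6225]² / 0.0225 = 137.9, so 138.

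This agrees with Table 1, and power at 138 per arm is 80.0%. The sample size is not in question.

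**2. How often the rule would admit VL.** The SE of a standardised difference is √(2/138) = 0.120. "Looks imbalanced" has no numerical definition in the SAP, so a cut-off must be assumed. The lean towards inclusion points to a low one.
- Cut-off 0.05 SD: z = 0.05/0.120 = 0.415, so VL enters in about 68% of trials and is left out in about 32%.
- Cut-off 0.10 SD: z = 0.831, so VL enters in 40.6% and is left out in about 59%.

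These proportions do not depend on how prognostic VL is.

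**3. Power.** The SAP gives no prognostic strength for entry VL, so the odds ratio (OR) per SD of log10 VL is assumed at 1.3, 1.5 and 2.0. The simulation used 20,000 replicates, n = 276, stratified 1:1 allocation and marginal risks of 35% and 20%. Log10 VL was N(4,1) truncated at log10(400), standardised, and independent of the strata. The stratum mix was country 50/50, age 50/50 and ART class 20/30/50. All of these except n, the allocation, the risks and the 400 c/mL limit are assumptions.

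| OR per SD | Stratum effect | Strata only | Rule, 0.10 SD | VL always | Gain over strata only | Gain over rule |
|---|---|---|---|---|---|---|
| 1.3 | none | 80.6% | 80.9% | 81.1% | 0.5 | 0.2 |
| 1.5 | none | 80.6% | 81.1% | 81.7% | 1.1 | 0.6 |
| 2.0 | none | 80.9% | 82.7% | 84.4% | 3.5 | 1.7 |
| 1.3 | OR 1.5 | 81.4% | 81.5% | 81.8% | 0.4 | 0.3 |
| 1.5 | OR 1.5 | 81.6% | 81.9% | 82.5% | 0.9 | 0.6 |
| 2.0 | OR 1.5 | 81.3% | 83.2% | 84.8% | 3.5 | 1.6 |

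The Monte Carlo SE of each paired difference between VL always and strata only is at most 0.23 points.

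Smaller runs without strata (6,000 trials per setting) gave gains over no VL adjustment of 0.2 / 1.4 / 3.1 points. Over the rule at cut-offs of 0.05 to 0.10 SD they gave 0.2–0.3 / 0.3–0.7 / 0.6–1.3 points. A further run without strata (20,000 replicates) at 0.05 SD alone gave 0.1 / 0.3 / 0.8 points, so the low end is close to nothing.

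**4. Precision of the risk difference.** Variance with VL always in, relative to strata only, is 0.99 / 0.97 / 0.91. The 95% CI half-width goes from 10.3 points to 10.2 / 10.1 / 9.8.

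**5. Type I error** (35% in both arms, VL OR 1.5 / 2.0): strata only 5.1 / 5.0%; rule at 0.10 SD 4.9 / 4.6%; VL always 5.2 / 5.1%. The rule is not anti-conservative.

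**6. An older sample.** Suppose current VL has OR 2.0 but the recorded value correlates with it at 0.7 or 0.5 (assumed). The effective OR is then 2^0.7 = 1.62 or 2^0.5 = 1.41. Power over strata only goes from 80.8% to 82.5% (+1.7) or from 80.4% to 81.2% (+0.8). Over the rule at 0.10 SD the gain is about 0.7 or 0.4 points.

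**The case against.** The strongest reply is that nothing here is wrong: covariates are chosen before outcome data are seen, they must be relevant as well as imbalanced, and the rule leans towards inclusion. The shells only illustrate, so VL may be inspected and may enter. The gain depends on a prognostic strength that the SAP does not give, and several features could weaken it:
- A missing VL counts as an event whatever the reason (6.1).
- Entry VL is cut off below 400 c/mL.
- The sample may be almost four months old at screening.
- Any correlation of VL with country, age or ART class would mean that the strata already carry part of its information.

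Most of this stands. It limits the size of the point and removes any charge of invalidity. It does not answer two things. Leaning towards inclusion still applies only to covariates seen as imbalanced, so a prognostic but balanced VL stays out. And without a list or a threshold the primary model remains open until the baseline data have been viewed.

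A reader might infer that choosing covariates by eye inflates false positives, or that the plan forbids adjusting for VL. The simulated type I error contradicts the first and the wording of section 8 the second.

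**Conclusion.** This is a cheap improvement of modest size, not an error of validity. For an assumed OR per SD of 1.3 to 2.0, always including entry VL gains about 0.2 to 3.5 points of power over strata only. Over an inclusive reading of the rule (cut-off about 0.05 to 0.10 SD) it gains about 0.2 to 1.7 points. The variance of the risk difference falls by about 1% to 9% against strata only. The firmer benefit is a primary model fixed in advance.

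Larger figures can be produced, but the SAP does not support them. An OR of 3.0 per SD gives about 7 points over strata only. With the simulated SD of 0.865 log10, that means 3^(1/0.865) ≈ 3.6-fold odds per tenfold VL, and nothing in the SAP points to an effect that strong. Cut-offs of 0.20 or 0.25 SD would leave VL out in about 90% or 96% of trials, but they sit badly with the stated lean towards inclusion. In the other direction, if VL is not prognostic there is no gain, and an older sample shrinks it.

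**What to change.** In 6.2, pre-specify the primary model as arm + country + age stratum + ART class + log10 of the latest pre-randomisation VL, whatever the observed balance, and derive the risk difference from that model. Move adjustment for visually imbalanced covariates (5.4) to a sensitivity analysis. Add baseline VL (median, IQR) to Table 8.3. In the same sentence of 6.2, correct the reference to a section 5.5, which does not exist (the rule is in 5.4), and the word for clusters, since individuals are randomised. Section 3.5, which limits the interim model to the strata, can stay.

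The cost is wording in 5.4 and 6.2, one table row and one model term. The conditional odds ratio moves somewhat further from 1 (simulated median from 0.46 to 0.45 / 0.44 / 0.42 for OR per SD 1.3 / 1.5 / 2.0). The SE of the log odds ratio rises from 0.283 to 0.286 / 0.289 / 0.300. A single linear log10 term is itself an assumption.

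One thing must be confirmed. Randomisation takes place "once eligibility and consent have been confirmed and entered into the database", but the SAP does not say that the numeric VL is stored rather than only the fact that the criterion was met. If it is stored, no new measurement is needed.

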6.1 Outcome definitions

The VL of participants who did not have a VL measured for the primary and secondary endpoints within the required window will be considered as missing. This includes not having a visit within the respective window, visits without a blood draw, and blood draws with no result available. Missing VL will be counted as having achieved the primary endpoint, i.e. considered as an unsuppressed VL. Clarification of secondary and other outcome definitions are provided in section 3.1.2.

6.2 Analysis methods

Continuous variables will be inspected using histograms: 1) to assess for outliers which may be queried for accuracy, and 2) to assess whether appropriate transformations are required for modeling.

Endpoints will be summarized using medians and interquartile ranges for continuous variables and numbers and percentages for categorical variables, by randomized group. Percentages will be reported to one decimal place.

We will present numbers and proportions of participants achieving each of the four components of the composite endpoint separately. Those with missing VL results will be handled as

described in section 6.1 and reasons for missing VL results will be provided.

For the analysis of the primary outcome, we will use a logistic regression model adjusted for the randomization stratification factors (country, age, and ART regimen; see section 3.2) and relevant baseline characteristics found to be unbalanced between intervention and control clusters (as described above in section 5.5). Results will be reported as odds ratios with 95% confidence intervals. Further, we will estimate the absolute risk difference, with 95% confidence intervals estimated using the delta method [7].

Sensitivity analyses

In a first sensitivity analysis for the primary outcome, we will analyze the PP set (see section 4.2). Protocol violations and deviations will be described. We will summarize the data (numbers and proportions of participants included in this analysis, and meeting the primary endpoint), and fit logistic regression models as for the main primary outcome analysis.

As a second sensitivity analysis of the primary outcome, we will also consider an additional two definitions of viral suppression - <400 and <1000 copies/mL.

Subgroup analysis

Effect modification of the primary endpoint by country (Lesotho or Tanzania), gender (male or female), age ([\geq 6 months to <12 years] or [\geq 12 years to <19 years]), and ART regimen at enrolment (NNRTI-, PI-, or INSTI-based regimen) will be assessed by incorporating an interaction between arm and the effect modifier acknowledging that power will be low. Regimens at enrolment containing more than one of the above-mentioned ART types will be classified as INSTI-based if they contain at least one INSTI as well as one or more PI(s) and/or NNRTI(s), and as PI-based if they contain at least one PI and one or more NNRTI(s). If there are small numbers of participants within certain subgroups, then such an approach may not be feasible and instead we would restrict the model to the subgroups of sufficient size. If the interaction term is found to be significant, effect estimates will be summarized by subgroup. As the study is not powered for these pre-planned subgroup analyses, these results will be considered exploratory.

Secondary endpoints

For the secondary endpoints defined by the individual components of the composite outcome, we will summarize the number and proportion of participants meeting each endpoint definition as described in 3.1.2. We will follow the same approach as for the main primary outcome analysis if numbers allow, otherwise we will compare the endpoints between the study arms using a chi-squared or Fischer's exact test (in the case of limited events).

For the remaining secondary endpoints, we will follow the same approach as for the main primary outcome analysis if numbers allow. All analyses of secondary outcomes will be done on the mITT set.

Exploratory endpoints

If the number of events is sufficient, the exploratory endpoint of time to documented viral suppression will be assessed using Kaplan Meier estimation and Cox proportional hazard models adjusted for the stratification factors, reporting hazard ratios and 95% confidence intervals.

The exploratory endpoints of drug regimen switches and emergence of new drug resistance mutations will be compared between the study arms using a chi-squared or Fischer's exact test (in the case of limited events).

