3.3 Sample size

The sample size was estimated with the aim of showing a significant reduction of the composite primary endpoint in the intervention arm compared to the control arm. The significance level was chosen to be 5%, while the power was chosen to be at least $(1-\beta) = 80\%$.

Based on the available literature and own experience at the study sites, we compared various realistic scenarios of what ratio of participants would reach the primary endpoint in each study arm (see Table 1).

Table 1: Sample size for different scenarios with 80% power and $\alpha = 0.05$.

Difference ^a	PInt	PC	n (per arm)
20%			
	0.25	0.45	89
	0.20	0.40	82
	0.15	0.35	73
15%			
	0.25	0.40	152
	0.20	0.35	138
	0.15	0.30	121

^a Reduction of the event rate for the treatment group compared to the control group. PInt: Probability of event in the intervention group; PC: Probability of event in the control group.

As our hypothesis for the sample size calculation, we selected the scenario in which 20% vs 35% of participants reach the primary endpoint in the intervention vs the control arm. Using a Pearson's chi-squared test with a significance level of 5% and a power of 80%, a required sample size of calculated (see Table 1).

Participants prematurely leaving the study will not be replaced.

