6.3 Missing data

Where applicable, percentages of baseline and endpoint data will be of non-missing values, with the number (%) of missing values given if data are not complete. As detailed in section 6.2, main analyses of the primary and the secondary outcomes (with the exception of virological failure) will include all participants as randomized with missing virological data counted as failures.

For the secondary outcome of unobserved virologic failure, only individuals with a valid viral load result in the specified window will be included in the analysis.

Where significant amounts of data are missing in important covariates, we may consider multiple imputation as sensitivity analyses if necessary and compare results to models ignoring missing data [8].

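### The Kaplan-Meier analysis of time to documented suppression has no rule for death; one minus Kaplan-Meier would modestly overstate cumulative suppression (minor, exploratory endpoint only)

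*SAP*

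**What the plan says.** SAP section 3.1.2 lists time to viral resuppression below 50 c/mL as the first exploratory endpoint, read from samples at the 3-, 6- and 9-month visits. Section 6.2 gives its analysis, to be run only if there are enough events: "time to documented viral suppression will be assessed using Kaplan Meier estimation and Cox proportional hazard models adjusted for the stratification factors", with hazard ratios and 95% confidence intervals. Neither section states a censoring rule or says what happens to a participant who dies before suppressing.

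Death is an expected outcome in this plan. Component (i) of the primary composite in section 3.1.2 is "death due to any cause during the follow-up period (36 weeks"), and death is also a secondary endpoint in its own right.

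A rule for absent viral loads exists for other endpoints. Section 6.1 says "Missing VL will be counted as having achieved the primary endpoint, i.e. considered as an unsuppressed VL". Section 6.3 repeats the principle ("missing virological data counted as failures") for the primary and secondary outcomes, except virologic failure, which is analysed only in those with a valid result. Exploratory endpoints are not named in either section.

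**The concern.** The event here is favourable, and death rules it out. Ordinary Kaplan-Meier removes a participant who dies unsuppressed from the risk set. It then in effect gives that person the later chance of suppression seen in survivors. That would be reasonable if the person could still suppress after being censored, but a participant who has died cannot. One minus Kaplan-Meier therefore does not estimate the proportion of randomised participants who reach documented suppression, although readers will take the curve to show exactly that.

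What is at stake is limited but real. The dynamics of resuppression are a stated exploratory objective, and this curve is the planned analysis of them. A standard estimator avoids the problem, and the choice is best fixed before data are seen, since the trial is open-label.

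**Working it through.** **The plan's own figure.** The SAP states no figure for this endpoint. Its design figure is 138 per arm (section 3.3, Table 1: 20% vs 35%, 5% significance, 80% power; two-sided per section 4.1; 1:1 per section 3.2):

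n = [1.960 × √(2 × 0.275 × 0.725) + 0.842 × √(0.20 × 0.80 + 0.35 × 0.65)]² / 0.15² = 137.9, so 138.

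It reproduces. The point does not bear on it; 138 is used below only to turn percentages into numbers of participants.

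**Assumed inputs (none is in the SAP).**
- Suppression among those alive and unsuppressed: s = 40%, 35% and 30% at months 3, 6 and 9.
- Deaths per interval among the unsuppressed: d = 0.5% to 2%, each falling before the next visit.
- No losses, so that the effect of death stands alone.

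**One minus Kaplan-Meier, deaths censored.** Each visit's factor uses only those still at risk, so d drops out:

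1 − (0.60 × 0.65 × 0.70) = 1 − 0.273 = 0.727.

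**Cumulative incidence, deaths counted as never suppressed.** Start with u₀ = 1. At each visit the number at risk is a = u × (1 − d), the events are e = a × s, and the new u is a − e. The cumulative incidence is the sum of e.

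| Visit | d = 0.5%: a, e, u | d = 2%: a, e, u |
|---|---|---|
| Month 3 | 0.9950, 0.3980, 0.5970 | 0.9800, 0.3920, 0.5880 |
| Month 6 | 0.5940, 0.2079, 0.3861 | 0.5762, 0.2017, 0.3746 |
| Month 9 | 0.3842, 0.1153 | 0.3671, 0.1101 |
| Sum of e | 0.721 | 0.704 |

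Overstatement: 72.7 − 72.1 = 0.6 points, and 72.7 − 70.4 = 2.3 points.

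**What these rates mean for an arm of 138.** Deaths before suppression are d × (u₀ + u₁ + u₂) × 138:
- 0.005 × (1 + 0.5970 + 0.3861) × 138 = 1.4 deaths;
- 0.02 × (1 + 0.5880 + 0.3746) × 138 = 5.4 deaths.

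**Second set of assumptions.** Take a constant suppression probability per visit, set so that 65% or 80% of those who stay suppress by month 9 (the complements of the 35% and 20% design rates). Let a total exit probability t be spread evenly, 1 − (1 − t)^(1/3) per interval, and read every exit as a death.

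| Total exits | 65%: cumulative incidence (gap) | 80%: cumulative incidence (gap) |
|---|---|---|
| 1% | 64.6% (0.4) | 79.6% (0.4) |
| 2% | 64.2% (0.8) | 79.1% (0.9) |
| 5% | 63.1% (1.9) | 77.8% (2.2) |

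The size agrees with the first set: under 1 point when deaths are very few, about 2 points at 5%.

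**Effect on the arm comparison.** With equal exits in both arms, the 15-point Kaplan-Meier difference (80% vs 65%) becomes 14.9 points at 2% exits and 14.7 at 5%. The error is mainly in the level of each curve, not in the contrast.

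**The case against.** The strongest reply is that the SAP states no censoring rule, so it cannot be said to use a wrong one. Carrying deaths forward as unsuppressed to the end of the 9-month window would also fit the words of section 6.2. This stands in part: that deaths are censored is an inference from ordinary practice. But a plan that names Kaplan-Meier without further instruction will normally be coded that way.

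A reader might draw stronger conclusions, which the documents do not support:

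- **That censoring contradicts sections 6.1 and 6.3.** It does not. The missing-as-failure rule covers primary and secondary outcomes only, and section 6.3 itself exempts one secondary outcome. Nor would a mismatch with the month-9 viral-load component show an error: someone suppressed at month 3 who rebounds by month 9 is an event in one analysis and a failure in the other.
- **That differences in death or retention are hidden.** They are not hidden at trial level. Death and loss to follow-up are each secondary endpoints compared by arm, and the primary composite counts both death and a missing 9-month viral load as failure.
- **That the Cox hazard ratio is wrong.** With deaths censored it is a valid cause-specific hazard ratio, which suits a question about the dynamics of resuppression. Keeping the dead in the risk set would mix mortality into it.
- **That the overstatement is much larger.** Adding loss of 3% to 6% per interval to the deaths lowers the proportion to between 68.7% (0.5% deaths, 3% loss) and 63.8% (2% deaths, 6% loss), a gap of 4.0 to 8.9 points. That counts everyone lost as never suppressed. Someone who left care may have suppressed without a test, so this is a choice of what to estimate, not a bias in the plan.

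**Conclusion.** The point holds as a minor one, confined to one exploratory endpoint that is analysed this way only if events suffice. Death is a competing event for suppression, section 6.2 does not provide for it, and one minus Kaplan-Meier with deaths censored is too high as the proportion reaching documented suppression. The overstatement of about 0.6 to 2.3 points rests on assumed suppression and death rates. With almost no deaths it would be negligible. The cumulative incidence estimate is nevertheless the better method, because it is right whatever the number of deaths.

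**What to change.** In section 6.2, under the exploratory endpoints:

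1. Replace one minus Kaplan-Meier with the cumulative incidence of documented suppression by arm, estimated by Aalen-Johansen with death before suppression as a competing event.
2. Keep the Cox model adjusted for the stratification factors, state that deaths are censored in it, and label its hazard ratio cause-specific.
3. State how participants lost while unsuppressed are handled. Optionally, show two versions side by side: censored at the last viral load, and kept in the risk set as unsuppressed to the end of the 9-month window.

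The cost is a few sentences of SAP text and a few lines of Stata code, with no new data. The cumulative incidence curve will reflect mortality as well as resuppression, which is why the cause-specific hazard ratio should stand beside it. The small downside of the optional version that keeps losses at risk is that it mixes retention with resuppression, so it belongs in a sensitivity analysis.
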